5.9 Subject Replacement Strategy

Patients who do not complete at least one cycle of therapy will be replaced.

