8.1.1 Analysis Populations

8.1.1.1 Definition of Populations

Full Analysis

The Full Analysis (FA) population includes all patients who received at least one cycle of pembrolizumab and had at least one valid post-baseline efficacy assessment. The FA population will be used for all listings of raw data. Unless otherwise specified, the FA population will be the default analysis set used for all analyses.

Safety

The safety population includes all patients (primary and exploratory cohorts) who received at least one cycle of pembrolizumab and have at least one valid post-baseline safety assessment.

Per Protocol

The Per-Protocol (PP) population will consist of a subset of patients in the FA population who completed 6 treatment cycles and did not have major protocol violations or deviations. This population will be the secondary population for the analysis of the primary efficacy endpoint.

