8.1.1.2 Applicability of Population Efficacy analyses

- The primary efficacy analysis of clinical improvement (CI) or better (partial response (PR) or complete response (CR)) as shown in TABLE 5, will be based on the FA population. A secondary analysis of CI or better (PR or CR) will be performed on the PP population.
- All secondary efficacy analyses will be performed for the FA population.

Product: MK-3475
Protocol/Amendment No.:

Safety analyses

All safety analyses will be based on the safety population. In addition, specific assessments of late toxicity will be performed for patients in the safety population who are followed for safety for at least one year from treatment initiation.

Exploratory analyses

Biomarker analyses will be performed in patients for the FA population.

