8.2 Statistical Analysis Methods

Description of Data

Data will be presented in patient data listings by patient and according to visit. Continuous variables will be summarized using standard summary statistics such as number of observations (n), mean value, standard deviation (SD), minimum and maximum values, median value, and 1st and 3rd quartiles. Categorical variables will be summarized in frequency tables as counts and percentages. All individual data collected in the CRFs will be presented in data listings. Patients screened but not included in the study (i.e. screen failures) will not be presented in any tables or listings.

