8.2.3 Analysis of Safety Endpoints

All safety summaries will be presented for the safety population. No formal statistical analysis of safety endpoints will be performed. Safety data to be evaluated includes AEs, physical examination and clinical laboratory results.

The overall observation period will be divided into three mutually exclusive segments:

1. Pre-treatment period: from day of patient's informed consent to the day before first dose of study medication.
2. On-treatment period: from day of first dose of study medication to 30 days after last dose of study medication.
3. Post-treatment period: starting at day 31 after last dose of study medication.

If dates are incomplete in a way that clear assignment to pre-, on-, post-treatment period cannot be made, then the respective data will be assigned to the on-treatment period.

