8.2.3.1 Adverse Events (AEs)

Summary tables for adverse events (AEs) have to include only AEs that started or worsened during the on-treatment period, the treatment-emergent AEs. However, all safety data (including those from the pre and post-treatment periods) will be listed and those collected during the pre-treatment and post-treatment period are to be flagged.

The incidence of treatment-emergent adverse events (new or worsening from baseline) will be summarized by system organ class and or preferred term, severity (based on CTCAE grades), type of adverse event, relationship to study treatment.

Deaths reportable as SAEs and non-fatal serious adverse events will be listed by patient and tabulated by type of adverse event.

Specific safety event categories (SEC) will be considered. Such categories consist of one or more well-defined safety events which are similar in nature and for which there is a specific clinical interest in connection with the study treatment(s).

For each specified SEC, number and percentage of patients with at least one event within the SEC will be reported.

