11.3 Safety Stopping Rules

Sponsor and DBMB will meet quarterly to review the patient data for safety as related to the stopping rules as defined in this section.

If a patient experiences grade 3 or higher toxicities (excluding grade 3/4 hematologic toxicity) deemed at least possibly related to the study drug (and not clearly disease related), or if grade 2 laboratory (excluding grade 2 hematologic toxicity) or clinical toxicities deemed at least possibly related to the study drug (and not clearly disease related) do not resolve within 3 weeks in spite of treatment, we will stop study drug administration.

If, among the MF-CP (primary cohort) patients, 3 or more of the first 5, 4 or more of the first 10, 6 or more of the first 15, or 7 or more of the first 24 patients stop study drug within the first 3 cycles due to toxicity as defined above in the previous paragraph, we will stop

Product: MK-3475

Protocol/Amendment No.:

enrolling patients to the primary cohort. The probability of stopping early if the true toxicity rate is 20%, 30%, 40% or 45% is 0.18, 0.51, 0.81, 0.91, respectively.

If, among the MPN-AP/BP (exploratory cohort) patients, 2 or more of the first 5 or 3 or more of the first 10 patients, stop study drug within the first 3 cycles [due to toxicity as defined above in the previous paragraph](#), we will stop enrolling patients to the exploratory cohort. The probability of stopping early if the true toxicity rate is 20%, 30%, 40% or 50% is 0.26, 0.48, 0.66, 0.81, respectively.

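### The safety population is not defined by any dose, so first-cycle toxicity can drop out of the safety tables; the listing set and the counting of replaced patients also need reconciling

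*Combined protocol and SAP*

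**What the plan says.** **Safety set.** Section 8.1.1.1 limits the safety population, for both cohorts, to patients "who received at least one cycle of pembrolizumab and have at least one valid post-baseline safety assessment". Section 8.1.1.2 adds "All safety analyses will be based on the safety population", and Section 8.2.3 adds "All safety summaries will be presented for the safety population".

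**Listings.** Section 8.1.1.1 states "The FA population will be used for all listings of raw data". The FA population needs at least one cycle and a valid post-baseline efficacy assessment. Section 8.2 states "All individual data collected in the CRFs will be presented in data listings" and leaves out only screen failures. Section 8.2.3.1 states "all safety data (including those from the pre and post-treatment periods) will be listed", and also lists reportable deaths and non-fatal serious events by patient.

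**Replacement and stopping rule.** Section 5.9 states "Patients who do not complete at least one cycle of therapy will be replaced", with no exception for toxicity and nothing on how such a patient is counted. Section 11.3 halts enrolment when set numbers of the first 5, 10, 15 or 24 primary-cohort patients (first 5 or 10 in the exploratory cohort) "stop study drug within the first 3 cycles due to toxicity as defined above in the previous paragraph".

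**The concern.** Both entry conditions for the safety population depend on what happens after the first infusion, so toxicity itself can cause exclusion. A safety set should be fixed by exposure alone. The patients most at risk of being lost are those with the earliest and most severe events. Section 3.4 makes safety an objective in both cohorts, and with at most 24 and 10 patients a single missing case is 4.2 (1/24) or 10 (1/10) percentage points.

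The listing and replacement texts bear on the same patients. If the listings followed the FA set, the usual backstop for a patient missing from the tables would be uncertain. If a replaced patient left the Section 11.3 count, that rule would lose part of its ability to detect early toxicity. Neither result is stated in the plan, and neither is excluded by it.

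**Working it through.** **1. Who can be left out of the tables.** Section 2.1 makes a cycle three weeks. Section 5.2 (Table 2) gives the drug only on Day 1. Section 8.1.1.1 speaks of a cycle being received, and does not say whether that means the infusion or the three weeks.

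- *Three-week reading.* A patient who stops or dies in cycle 1 fails the first condition and is absent from every safety table.
- *One-infusion reading.* That patient meets the first condition. What remains is a partial infusion, or a finding that there was no valid assessment. The word valid is not defined. The flow chart in Section 6.1 has no clinic visit between the cycle 1 and cycle 2 doses, but Section 5.2.2 requires post-infusion vitals and calls during cycle 1, and Section 7.2 records adverse events from consent.

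**2. Size in the tables (counts assumed for illustration).** With *k* severe cases among *n* dosed patients and *m* of them excluded, the table shows (*k* − *m*)/(*n* − *m*) instead of *k*/*n*. For *k* = 7, *n* = 24, *m* = 2: 5/22 = 22.7% instead of 7/24 = 29.2%.

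**3. Stopping rule as written, every patient counted.** Boundaries from Section 11.3: primary at least 3/5, 4/10, 6/15, 7/24; exploratory at least 2/5, 3/10. The calculation is exact sequential binomial, in which a path that reaches a boundary is stopped there.

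| Cohort | True rate | Stated in 11.3 | All written looks |
|---|---|---|---|
| Primary | 20% | 0.18 | 0.247 |
| Primary | 30% | 0.51 | 0.658 |
| Primary | 40% | 0.81 | 0.919 |
| Primary | 45% | 0.91 | 0.969 |
| Exploratory | 20% | 0.26 | 0.389 |
| Exploratory | 30% | 0.48 | 0.669 |
| Exploratory | 40% | 0.66 | 0.860 |
| Exploratory | 50% | 0.81 | 0.955 |

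The stated figures do not reproduce. The primary ones agree with a last look of 7 of 20 instead of 7 of 24 (0.175, 0.506, 0.813, 0.906). The exploratory ones agree to within 0.01 with the first look alone (0.263, 0.472, 0.663, 0.813). This is a separate discrepancy that Section 11.3 must reconcile. The baseline below is the rule as written.

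**4. If replaced patients were not counted.** Let *p* be the true rate of toxicity stops within three cycles and *f* the share of them that fall before cycle 1 is completed. The rate among counted patients is *p*(1 − *f*)/(1 − *pf*). The documents give no value for *f*; a range of 10% to 50% is assumed. At *p* = 0.40:

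- *f* = 0.10: 0.36/0.96 = 0.375
- *f* = 1/3: 0.267/0.867 = 0.308
- *f* = 0.50: 0.20/0.80 = 0.250

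| *f* | Counted rate | Primary, all looks | Exploratory, all looks |
|---|---|---|---|
| 0 | 0.400 | 0.919 | 0.860 |
| 0.10 | 0.375 | 0.876 | 0.822 |
| 1/3 | 0.308 | 0.687 | 0.687 |
| 0.50 | 0.250 | 0.453 | 0.537 |

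At *p* = 0.30 the primary figure falls from 0.658 to between 0.573 and 0.167, and the exploratory figure from 0.669 to between 0.614 and 0.318.

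The 24th patient completes the primary cohort, so a look there may come too late to save enrolment. Using only the looks at 5, 10 and 15, the primary figure at *p* = 0.40 falls from 0.709 to 0.643 (*f* = 0.10), 0.443 (*f* = 1/3) and 0.273 (*f* = 0.50). The seventh event can occur before patient 24, so the four-look figures are used for the conclusion.

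**The case against.** A reader might infer that an early severe event disappears from the tables, the listings and the stopping count together, all because of the safety-population definition. The documents do not support that.

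- *Listings.* Sections 8.2 and 8.2.3.1 say that all case-report data and all safety data are listed. The FA sentence contradicts them, but does not establish a loss.
- *Stopping count.* Section 11.3 names neither the safety nor the FA population. Its window is the first three cycles, so on plain reading a cycle 1 toxicity stop counts. The only route out is the silence of Section 5.9. Oversight does not depend on analysis sets either: Section 11.1 has serious events reviewed as they occur and adverse events quarterly, and Section 5.10 allows termination for adverse reactions.
- *Full cycle.* Section 8.1.1.1 says received for the safety set but completed for the per-protocol set, and Section 5.9 also speaks of completing. That contrast favours the one-infusion reading. The contacts required in cycle 1, and the final-visit procedures at discontinuation in Section 7.1.4.1, would usually supply a post-baseline assessment.
- *Size.* It would also go too far to say that two early cases among 34 patients turn 5.9% into 0%. That needs no other severe case among those retained, and it pools cohorts that Section 8.1 summarises separately.

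These points stand, and they limit the concern. They do not remove it. The plan does not choose between the two readings of a cycle, does not define a valid assessment, and leaves the listing conflict and the counting question open. Such choices should not be made after it is known which patients had early events.

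**Conclusion.** The concern holds for the safety tables. The definition conditions on events after dosing, and on the three-week reading it removes patients stopped by first-cycle toxicity and biases incidence downward. On the one-infusion reading the remaining gap is small.

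The listings point is a contradiction within Section 8. The stopping-count point is an ambiguity between Sections 5.9 and 11.3, not a consequence of the population definition. Only if replaced patients went uncounted would the chance of stopping at a true 40% rate fall, under all written looks, from 0.92 to between 0.88 and 0.45 (primary) and from 0.86 to between 0.82 and 0.54 (exploratory). Those ranges rest on the assumed 10% to 50% share of stops in cycle 1, on every such patient being replaced and uncounted, and on independent patients with a common rate.

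Severity: should be corrected, below must-fix.

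**What to change.** 1. Section 8.1.1.1: define the safety population as every patient who received any amount of pembrolizumab, with no post-baseline condition.
2. Sections 8.1.1.1, 8.2 and 8.2.3.1: remove the conflict by stating that safety listings use that any-dose set.
3. Sections 5.9 and 11.3: state that a replaced patient stays in the safety population and, for the stopping rule, in both the numerator and the first-*n* count, taken in order of first dose.

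While Section 11.3 is open, its stated probabilities should be reconciled with its written boundaries.

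The cost is a few sentences and no new data. Reported toxicity rates may be slightly less favourable. If the sponsor already intends this handling, the wording only records it.

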8.1.1.2 Applicability of Population Efficacy analyses

- The primary efficacy analysis of clinical improvement (CI) or better (partial response (PR) or complete response (CR)) as shown in TABLE 5, will be based on the FA population. A secondary analysis of CI or better (PR or CR) will be performed on the PP population.
- All secondary efficacy analyses will be performed for the FA population.

Product: MK-3475
Protocol/Amendment No.:

Safety analyses

All safety analyses will be based on the safety population. In addition, specific assessments of late toxicity will be performed for patients in the safety population who are followed for safety for at least one year from treatment initiation.

Exploratory analyses

Biomarker analyses will be performed in patients for the FA population.

8.2 Statistical Analysis Methods

Description of Data

Data will be presented in patient data listings by patient and according to visit. Continuous variables will be summarized using standard summary statistics such as number of observations (n), mean value, standard deviation (SD), minimum and maximum values, median value, and 1st and 3rd quartiles. Categorical variables will be summarized in frequency tables as counts and percentages. All individual data collected in the CRFs will be presented in data listings. Patients screened but not included in the study (i.e. screen failures) will not be presented in any tables or listings.

8.2.1 Patient demographics and other baseline characteristics

Demographic data and other baseline characteristics (including medical and disease history) will be summarized using descriptive statistics.

8.2.2 Analysis of Efficacy Endpoints

8.2.2.1 8.2.3.1 Primary Endpoint

The primary efficacy endpoint, CI or better (PR,CR) after 6 cycles of treatment as defined by the combined European Leukemia Net –International Working Group (ELN-IWG)) (Table 5) in patients with MF-CP (primary cohort) will be reported as a percentage of the total number of subjects enrolled for both FA and PP populations. A two-sided 90% exact confidence interval for the percentage will be computed using the Clopper and Pearson method.

8.2.2.2 8.2.3.2 Secondary Endpoints

The secondary efficacy endpoint, CRi or better (CR), after 6 cycles of treatment as defined by Acute Myeloid Leukemia Response criteria (Table 6A) in patients with MPN-AP/BP (exploratory cohort) will be reported as a percentage of the total number of subjects enrolled for the FA population.

Product: MK-3475

Protocol/Amendment No.:

The secondary endpoint, ALR-P or better (ALR-C, CCR, CMR), after 6 cycles of treatment as defined using published consensus criteria by Mascarenhas et al. (Table 6B) in patients with MPN-AP/BP (exploratory cohort) will be reported as a percentage of the total number of subjects enrolled for the FA population.

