The choice of the 200 mg Q3W as an appropriate dose for the switch to fixed dosing is based on simulations performed using the population PK model of pembrolizumab showing that the fixed dose of 200 mg every 3 weeks will provide exposures that 1) are optimally consistent with those obtained with the 2 mg/kg dose every 3 weeks, 2) will maintain individual patient exposures in the exposure range established in melanoma as associated with maximal efficacy response and 3) will maintain individual patients exposure in the exposure range established in melanoma that are well tolerated and safe.

A fixed dose regimen will simplify the dosing regimen to be more convenient for physicians and to reduce potential for dosing errors. A fixed dosing scheme will also reduce complexity in the logistical chain at treatment facilities and reduce wastage.

4.2.3 Study Design and Statistical Methods:

This is an open-label phase II trial to assess the efficacy, safety and tolerability of pembrolizumab in patients with PMF, post-PV MF, and post-ET MF. We propose a Simon

Two-Stage design for this study; the first 9 MF patients will be enrolled to confirm a signal of activity and safety of pembrolizumab at the FDA approved dose (in head and neck cancer) of 200mg administered via intravenous infusion over 30 minutes given every 3 weeks for six cycles.

In stage 1, if at least one response (out of 9 subjects in the primary cohort) is observed after six cycles of treatment at week 18, 15 additional patients will be accrued in the second stage (total of 24 evaluable patients in the primary cohort). If however, fewer than 3 of 24 patients respond to therapy, pembrolizumab will be deemed not worthy of any further investigation in this patient population. If response is seen in greater than or equal to 3 of 24 patients, pembrolizumab will be considered to have activity in this patient population and will be recommended for further study. For this study we define inactivity as a response rate of 5%, and activity as a response rate of 25%, which is comparable to that seen with ruxolitinib in a mixed population. The probability of erroneously concluding that the drug has activity if the true but unknown response rate is 5% is 0.10. The power to detect a response rate of 25% with this design is 0.90.

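### The 90% Clopper-Pearson interval in 8.2.2.1 is not exact for the two-stage design, and its level does not match the one-sided 0.10 rule, so at exactly 3/24 it contains the 5% null

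*Combined protocol and SAP*

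**What the plan says.** Section 4.2.3 sets the null rate at 5% and the target at 25%. The trial continues "if at least one response (out of 9 subjects in the primary cohort) is observed after six cycles of treatment at week 18", adding 15 patients for a total of 24. The final rule is: "If response is seen in greater than or equal to 3 of 24 patients, pembrolizumab will be considered to have activity". The stated error is: "The probability of erroneously concluding that the drug has activity if the true but unknown response rate is 5% is 0.10". For power: "The power to detect a response rate of 25% with this design is 0.90". Sections 8.3 and 11.4 repeat the stop at zero responses in nine, and 11.4 calls the design Simon's optimal.

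Section 8.2.2 says that the primary endpoint "will be reported as a percentage of the total number of subjects enrolled for both FA and PP populations". It then specifies the interval: "A two-sided 90% exact confidence interval for the percentage will be computed using the Clopper and Pearson method".

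No section gives an estimate or interval that allows for the interim stop. None relates the 90% level to the design error, and none says how the interval stands to the decision rule.

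**The concern.** Design and analysis use different sampling models. The error and power in 4.2.3 are two-stage probabilities. The interval in 8.2.2 is the one for a fixed sample of 24, in which the stop at 0/9 does not exist. Calling it exact claims guaranteed coverage of at least 90%, and that guarantee does not carry over to the two-stage design.

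The level is a second, independent mismatch. The rule tests 5% at one-sided 0.10, while a two-sided 90% interval corresponds to one-sided 0.05. A result between those two levels is declared active and yet has an interval that contains the rate defined as inactive. If that result occurs and the plan is silent, any interval or level chosen afterwards will look chosen to suit it.

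**Working it through.** **Inputs** (4.2.3, 8.2.2, 8.3): p0 = 0.05, p1 = 0.25; stage 1 of 9 patients, stop at 0; stage 2 of 15; active at 3 or more of 24; 90% Clopper-Pearson interval. If the trial stops, I take the interval as Clopper-Pearson on 0/9, which is 0 to 28.3%.

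**Step 1. Reproduce the plan's figures.** Let X be the final count in trials that pass stage 1.

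P(X = x) = Σ_{a≥1} b(a; 9, p) · b(x−a; 15, p), and P(active) = 1 − (1−p)^9 − P(X=1) − P(X=2).

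- At 5%: 1 − 0.63025 − 0.13831 − 0.13831 = 0.0931, within the stated limit of 0.10.
- At 25% the same sum gives 0.9028, against the stated 0.90.
- Without the interim stop, 3 or more of 24 would give 0.116 and 0.960. The plan's figures are therefore the two-stage ones.

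**Step 2. The two intervals.** For stage-wise ordering, rank 0/9 lowest and then the stage 2 totals upward. The lower limit solves P(X ≥ x; p) = 0.05. The upper limit solves (1−p)^9 + P(X ≤ x; p) = 0.05.

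| Result | Clopper-Pearson 90% | Stage-wise exact 90% |
|---|---|---|
| 3/24 | 3.5% to 29.2% | 3.8% to 32.1% |
| 4/24 | 5.9% to 34.2% | 6.1% to 35.6% |
| 5/24 | 8.6% to 38.9% | 8.7% to 39.6% |
| 6/24 | 11.5% to 43.5% | 11.6% to 43.8% |

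**Step 3. Coverage of the planned interval under the design.**

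- At 5%, only X ≥ 4 misses: 0.0931 − 0.0668 (the probability of exactly 3/24) = 0.0263. Coverage is 0.974. The stage-wise interval gives the same figure here.
- At 25%, coverage is 0.957.
- At 30%, the upper limit is too low after 0/9, 1/24, 2/24 and 3/24: 0.0404 + 0.0007 + 0.0060 + 0.0237 = 0.0708, against a nominal 0.05. Misses on the other side are 0.0314. Coverage is 1 − 0.0708 − 0.0314 = 0.898.
- At 29.3%, the same upper-limit sum is 0.0441 + 0.0009 + 0.0071 + 0.0272 = 0.0793.
- The minimum is 0.894, just above 29.2%, where the upper limit for 3/24 falls below the true rate. Coverage stays under 0.90 up to about 32%, and there is a very narrow dip near 44%.
- The stage-wise interval at 30% misses above only after 0/9, 1/24 and 2/24: 0.0404 + 0.0007 + 0.0060 = 0.0471. Over true rates from 1% to 60% its coverage stays at or above 0.90.

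**Step 4. The level.** The two-stage one-sided p-value against 5% at 3/24 is P(X ≥ 3; 0.05) = 0.093. It lies between 0.05 and 0.10, so a 90% two-sided interval must contain 5%, while a one-sided 90% lower limit excludes it: 5.16% with the two-stage calculation. Clopper-Pearson at that same level gives 4.68%, because its single-stage p-value is 0.116. At 4/24 the two-stage p-value is 0.026 and both 90% intervals exclude 5%.

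Exactly 3/24 has probability 0.17 at true rates of 10% and 15%, 0.12 at 20% and 0.06 at 25%.

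**Step 5. Point estimates at 3/24.** Raw: 3/24 = 12.5%. The unbiased two-stage estimate (UMVUE) is Σ C(8, a−1)·C(15, 3−a) / Σ C(9, a)·C(15, 3−a) over a = 1 to 3, that is (105 + 120 + 28)/(945 + 540 + 84) = 253/1569 = 16.1%. The median-unbiased estimate is 12.4%.

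**The case against.** The strongest reply is that nothing rests on this interval. Activity is decided by a count, and the plan gives the interval no part in that decision. Coverage exceeds 0.95 at both planning rates, and the worst shortfall is about half a percentage point. An interval that contains the null beside a positive count rule is no logical contradiction when the two work at different error levels, and the design never claimed one-sided 5%. All of that stands, and it is why the severity is low. It does not make the interval exact, and it does not fill the gap over how a 3/24 result should be read.

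A reader might infer two stronger points that do not hold:

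- **That ignoring the interim stop is why the interval at 3/24 contains 5%.** The two-stage exact 90% interval (3.8% to 32.1%) contains it too. The cause at the planned level is 5% per tail against a one-sided 0.10 rule.
- **That the raw rate taken into a next trial would be too low.** The raw proportion is biased low only when trials stopped at 0/9 are averaged in: by 2.0 points at a true rate of 5% and 1.2 points at 25%. Among trials that reach stage 2, which include every positive trial, it is biased high, by 3.2 points at 5% and 0.8 at 25%. At 3/24 the median-unbiased value is almost the same as the raw one.

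An 80% headline interval could also be seen as a level picked so that the boundary result just clears 5%. That is a fair criticism, so such an interval is not required here.

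**Conclusion.** The point holds as a low-severity reporting defect. The interval in 8.2.2.1 is labelled exact but ignores the stop at 0/9. The cost is coverage slightly below nominal at about 29% to 32%, with misses above the upper limit of 7% to 8% against 5%, and an upper limit at 3/24 that is 32.1 − 29.2 = 2.9 points too low. The level mismatch is separate and affects one positive outcome only, exactly 3/24.

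The decision rule, its error and its power are sound as stated. These figures assume that the design is run as written, with 9 then 15 patients and 24 in the analysis. If the analysed number differs, the limits must be recomputed.

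**What to change.** In 8.2.2.1:

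1. Replace Clopper-Pearson with the exact 90% interval based on stage-wise ordering for the two-stage design, recomputed if the final number is not 24.
2. State that activity is decided by the rule of 3 or more of 24.
3. Either add the one-sided 90% lower limit from the same two-stage calculation, which matches the design error of 0.10, or state that the 90% interval is descriptive.
4. Keep the raw count and percentage. A two-stage point estimate, unbiased or median-unbiased, is optional; if one is wanted, name it in advance.

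The cost is a few sentences and a short SAS program. The downside is a slightly higher upper limit at low counts. Sample size, conduct and the go/no-go rule are unchanged.
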